
Protocol ARC004 Synopsis	
Title	Peanut Allergy Oral Immunotherapy Study of AR101 for Desensitization in Children and Adults (PALISADE) Follow-On Study
	
Committee. Individual and cohort stopping rules are discussed further in Section 7.8.3.
 
End of Participation in ARC004 and Entry into ARC008:
 
After the end of participation in ARC004, subjects may enroll in the long-term, open-label extension study ARC008 to continue treatment with AR101 at their current dosing regimen (QD, BIW, QW, or QOW) or switch to AR101 daily dosing, until AR101 becomes commercially available or ARC008 is terminated, as follows:
 
• Subjects on any dosing regimen able to tolerate at least the 600 mg single dose of peanut protein (≥ 1043 mg cumulative) at their ARC004 Exit DBPCFC will continue their current dosing regimen in Treatment Pathway 1 of ARC008 when that study is available. If ARC008 is not available at the study site, these subjects may continue their current dosing regimen and have visits in ARC004 until they can enroll in ARC008.• Subjects who tolerate their nondaily dosing regimen and tolerate at least the 300 mg single dose of peanut protein (> 443 mg cumulative) but are unable to tolerate the 600 mg single dose of peanut protein (1043 mg cumulative) at the ARC004 Exit DBPCFC will switch to daily dosing with 300 mg AR101 in Treatment Pathway 1 of ARC008, per investigator discretion. If ARC008 is not available at the study site, these subjects may start AR101 daily dosing and have visits in ARC004 until ARC008 is available, then continue dosing in ARC008.• Subjects on a nondaily dosing regimen who tolerate less than the 300 mg single dose of peanut protein (443 mg cumulative) at the Exit DBPCFC may be eligible for treatment in ARC008 per investigator judgment and after discussion with the medical monitor. If continued treatment with AR101 is determined to be safe, these subjects will have the option to receive AR101 daily in Treatment Pathway 2 of ARC008, which consists of Repeat Up-dosing (dose escalation from 80, 120, or 160 mg to 300 mg daily), Initial Maintenance, and Extended Maintenance. If ARC008 is not yet available or able to accept these subjects at the study site, these subjects may start AR101 daily dosing and have visits in ARC004 until they can enroll in ARC008.• Subjects who do not tolerate their nondaily dosing regimen (described in study procedures for Extended Maintenance) will have the option to receive AR101 daily in Treatment Pathway 2 of ARC008, which consists of Repeat Up-dosing (dose escalation from 80, 120, or 160 mg to 300 mg daily), Initial Maintenance, and Extended Maintenance. If ARC008 is not available at the study site, these subjects may start AR101 daily dosing and have visits in ARC004 until ARC008 is available, then continue dosing in ARC008.• Subjects on a nondaily dosing regimen who miss or withhold their dose for > 3 days, including subjects receiving QOD, BIW, or QW dosing who miss or withhold their dose for > 14 days, will have the option to receive AR101 daily in Treatment Pathway 2 of ARC008, which consists of Repeat Up-dosing (dose escalation from 80, 120, or 160 mg to 300 mg daily), Initial Maintenance, and Extended Maintenance. If ARC008 is not available at the study site, these subjects may start AR101 daily dosing and have visits in ARC004 until they can enroll in ARC008.

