6.3.7 Double-Blind, Placebo-Controlled Food Challenge (Groups 1 and 2)

Group 1 subjects will undergo a Post-Maintenance DBPCFC, to be conducted in the same manner as the ARC003 Exit DBPCFC, but with a top dose of 2000 mg (4043 mg cumulative) peanut protein added, as shown in [Table 4](#).

All subjects in Groups 1 and 2 who complete their dosing regimen will undergo an Exit DBPCFC up to a single highest dose of 2000 mg of peanut protein (4043 mg cumulative), according to [Table 4](#). For subjects who do not tolerate their nondaily dosing regimen and subjects who switch to daily dosing after missing their nondaily dose for > 3 days, the Exit DBPCFC will be omitted before discontinuation from ARC004 and enrollment in ARC008. Subjects should not administer their AR101 dose on the day of the DBPCFC. All DBPCFCs will be conducted and evaluated based on PRACTALL guidelines. Sites will be provided a DBPFCFC manual, as in ARC003.

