- Group 2 combined cohorts B and C: QD, QOD, BIW, and Overall
- Group 2 Overall QD

Sponsor: Aimmune Therapeutics, Inc.

Protocol: ARC0004

Version: Version 1.0, 10Jul2019

For subjects in Group 2 who were not able to tolerate BIW or QOD dosing per study design and who subsequently reverted to a QD regimen, safety events for these subjects while on QD will be flagged in listings. Safety data collected after the dosing change will not be summarized in tables but will be presented in separate listings for key safety endpoints.

No summaries for any QW or QOW dosing regimens will be tabulated since no subjects initiated these dosing regimens.

All relevant data collected in the database and any derived data will be included in data listings and unless otherwise noted sorted by age group, group/cohort, subject number, test/measurement, and visit and time point as appropriate.

All statistical methods will be based on the International Conference on Harmonization (ICH)-E9 Guidance for Industry "Statistical Principles for Clinical Trials".

A review of the database will be conducted before database lock. Any decision to amend the planned statistical analysis will be documented in an amendment to the statistical analysis plan and details will be included in the CSR.

If the assumptions underlying the formal statistical methods proposed are not met during the analysis of the final data, an alternative, more appropriate, statistical method will be used and any changes documented in the statistical methods section of the CSR, including the rationale for use.

Additional exploratory analyses of the data will be conducted as deemed appropriate.

These analyses will be fully documented and clearly identified as post-hoc and exploratory.

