- Extended Maintenance (EM) period for Group 1 is defined as the time period beginning with the date and time of first dose of study product after the maintenance DBPCFC and ending with the date of the last dose of study product taken prior to Exit DBPCFC. Group 2 subjects will have undergone the Initial Dose Escalation, Up-dosing, and Maintenance Periods in ARC003 and will therefore enter the ARC004 EM period directly. The EM period for Group 2 is defined as the time period beginning with the date and time of first dose of study product in ARC004 and ending with the date of the last dose of study product taken prior to Exit DBPCFC. Length of EM period vary by group and cohort. See [section 2.3](#) for additional detail about each group and cohort.
- Exit DBPCFC period is defined as the time period beginning with the date and time of the first Exit DBPCFC dose and through 24 hours after the last dose of DBPCFC product.
- A DBPCFC is given in 2 parts, either on the same day, on consecutive days, or occasionally on non-consecutive days. For the non-consecutive days, the period of time more than 24 hours after the first part and before the second part begins will be attributed as follows
 1. For the Group 1 maintenance DBPCFC this is attributed to the Maintenance Period
 2. For the Exit DBPCFC Period it is attributed to the EM period.

Sponsor: Aimmune Therapeutics, Inc.

Protocol: ARC0004

Version: Version 1.0, 10Jul2019

- The active treatment period is defined as the time period beginning with the date and time of the first dose of study product in ARC004 and ending with the date and time of the last dose of study product in ACR004.
- Duration of active treatment period (days) is calculated as the date of last dose in ARC004 minus the date of first dose in ACR004 plus 1, excluding the DBPCFC periods.
- The Exit DBPCFC is defined as indeterminate if the subject was not able to tolerate the placebo challenge up to and including a dose of 2000 mg.

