10.1. STUDY TREATMENT EXPOSURE

Study treatment exposure will be summarized by age group (ages 4 to 17 and 18 to 55), group/cohort, and study period. The calculation of exposure will be based on in clinic dosing data and the dose level of the dispensed study medication.

First and last dose dates for each study period will be identified as follows:

| Study Period | Group/ Cohort | First Dose Date | Last Dose Date |
|-------------------------|--------------------------------|-----------------------------------------------------------------------------------------|----------------------------------------------------------------------------------------------------------------------------------------------------------------------------------------------------------------------------------------------------------------------------------------|
| Initial Dose Escalation | Group 1 | Date of first in-clinic dose at Initial Dose Escalation Day 1 | Date of last in-clinic dose at Initial Dose Escalation Day 1 or Day 2 |
| Up-Dosing | Group 1 | The day following the date study product was dispensed at Initial Dose Escalation Day 2 | Date of first in-clinic dose of 300 mg at the End Up-Dosing 300 mg Visit. For subjects who do not reach the 300 mg dose: the latest of the last in-clinic dose during the Up-Dosing period or the date of last study drug administration as entered on the Early Termination CRF page. |
| Maintenance | Group 1 | The day following the date study product was dispensed at End Up-Dosing 300 mg Visit | Latest of the last in-clinic dose during the Maintenance period or the date of last study drug administration as entered on the Early Termination CRF page |
| QD | Group 2, Cohorts 1, 3A, 3B, 3C | The first day of AR101 therapy in study ARC004 while on QD dosing | The last day of AR101 therapy in study ARC004 while on QD dosing |
| QOD | Group 2, Cohorts 2, 3B, and 3C | The first day of AR101 therapy in study ARC004 while on QOD dosing | The last day of AR101 therapy in study ARC004 while on QOD dosing |

Sponsor: Aimmune Therapeutics, Inc.

Protocol: ARC0004

Version: Version 1.0, 10Jul2019

| | | | |
|-----|--------------------------------------|--------------------------------------------------------------------------|----------------------------------------------------------------------|

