| BIW | Group 2, Cohorts 2, 3B, and 3C | The first day of AR101 therapy in study ARC004 while on BIW dosing | The last day of AR101 therapy in study ARC004 while on BIW dosing |
|-----|--------------------------------------|--------------------------------------------------------------------------|----------------------------------------------------------------------|

The total amount of study product consumed will be calculated as the sum of in-clinic doses plus the sum of doses taken at home as recorded in the diary.

The following calculations of study product exposure will be made and summarized:

- Duration of Exposure (in days and in months): calculated as the date of last dose of study product minus the date of the first dose of study product plus one during the study period. Duration of exposure will be summarized using descriptive statistics as well as categorically by the expected lengths of the overall treatment period.
- Total dose consumed (mg): calculated as the cumulative sum of all doses taken during the study period.
- Average dose per day (mg): calculated as the total dose consumed divided by the number of days during the study period.
- For Group 1 only: Maximum dose achieved (mg/day) during up-dosing using descriptive statistics for continuous data as well as categorically using all possible dose levels: 0.5, 1, 1.5, 3, 6, 12, 20, 40, 80, 120, 160, 200, 240, or 300 mg/day.
- For Group 1 only: Time to 300 mg dosing and time to 80 mg dosing for the overall treatment period using Kaplan-Meier methodology. Time will be calculated as date of the first 300 mg (or 80 mg) dose minus the first dose date +1. Subjects who do not reach the specified dose will be censored at the date of their last study product dose.

The non-missing valid diary entries will be used to estimate at-home dosing compliance. The following measures of compliance with at-home dosing will be calculated:

- Total number of planned at-home dosing days: calculated as the number of days where a valid diary entry was made, but excluding entries where a dose was missed because of doctor's orders.
- Percentage of planned dosing days where a full or partial dose was consumed.
- Percentage of planned dosing days where a full dose was consumed.
- Percentage of planned dosing days where a partial dose was consumed.
- Percentage of planned dosing days where a dose was missed.

Sponsor: Aimmune Therapeutics, Inc.

Protocol: ARC0004

Version: Version 1.0, 10Jul2019

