10.3. ADVERSE EVENTS

Treatment-emergent adverse events (TEAEs) will be summarized excluding symptoms recorded during the food challenges. The AE summaries will report AEs and in-clinic dosing symptoms.

If symptoms are recorded as part of an anaphylactic reaction, only the single anaphylactic reaction event will be summarized and not the individual symptoms.

All reported adverse events (AEs) will be classified into System Organ Class (SOC) and Preferred Term (PT) using Medical Dictionary for Regulatory Activities (MedDRA) version 19.1. The 5-point CoFAR severity grading scale was used for coding allergic reactions. The 3-point Muraro grading scale was used for grading the severity of anaphylactic reactions. The 5-point CTCAE severity grading scale was used for coding all other adverse events.

In Group 1, treatment-emergent adverse events are defined as those AEs with onset after the first dose of study product in ARC004 and no more than 30 days after the last dose of study product. In Group 2, as all patients are assumed to be continuing AR101 from study ARC003, all reported adverse events with onset no more than 30 days after the last dose of study product will be defined as treatment-emergent. Non treatment-emergent AEs will be included in subject listings, but not summarized. An additional summary of age group 18-55 will be included for the safety population for the overall AE summary and SAE summary.

Summaries that are displayed by system organ class and preferred terms will be ordered by descending incidence of system organ class and preferred term within each system organ class. Summaries displayed by preferred term only will be ordered by descending incidence of preferred term. Summaries of the following types will be presented:

- Overall summary of number of unique TEAEs and treatment-emergent serious adverse events (TESAEs), subject incidence of TEAEs and TESAEs meeting various criteria and exposure-adjusted incidence rates of TEAEs and TESAEs meeting various criteria, where exposure incidence rates are defined as the total number of events divided by the total number of subject-years at risk during the study period;
- Subject incidence of TEAEs by MedDRA system organ class and preferred term;
- Exposure-adjusted event rates for the most frequent TEAEs (i.e., TEAEs occurring in $\geq 5\%$ of the Safety Population) by MedDRA preferred term;

Sponsor: Aimmune Therapeutics, Inc.

Protocol: ARC0004

Version: Version 1.0, 10Jul2019

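### SAP 6.1 keeps post-switch daily-dosing safety data out of the tables only for subjects who could not tolerate BIW or QOD; switches due to the Exit food challenge or missed doses are not covered

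*SAP*

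**What the plan says.** **The exclusion.** SAP 6.1 covers Group 2 subjects "who were not able to tolerate BIW or QOD dosing per study design and who subsequently reverted to a QD regimen". Their safety data after the change are listed, not tabulated.

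**Who may switch.** The protocol (Synopsis and Section 3, on the end of participation and entry into ARC008) gives separate bullets to four kinds of nondaily subject who may return to daily dosing:

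1. those who do not tolerate the regimen, as defined in Section 7.8.2;
2. those who tolerate it and pass 443 mg but not 1043 mg at the Exit DBPCFC;
3. those below 443 mg at the Exit DBPCFC;
4. those who miss or withhold doses for too long.

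Each may take daily AR101 within ARC004 if ARC008 is not open at the site. For category 2 the text reads: "these subjects may start AR101 daily dosing and have visits in ARC004 until ARC008 is available". Protocol 6.3.7 also names category 4 apart from category 1: for "subjects who switch to daily dosing after missing their nondaily dose for > 3 days, the Exit DBPCFC will be omitted".

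**The dates.** SAP 10.1 ends the QD period for Cohorts 1, 3A, 3B and 3C at "The last day of AR101 therapy in study ARC004 while on QD dosing", and defines duration of exposure as "the date of last dose of study product minus the date of the first dose of study product plus one during the study period". For Group 2, SAP 10.3 says that "all reported adverse events with onset no more than 30 days after the last dose of study product will be defined as treatment-emergent". SAP 7.5 ends extended maintenance (EM) with a period "ending with the date of the last dose of study product taken prior to Exit DBPCFC". The primary-endpoint window closes at the end of EM in protocol 9.2.1 and at discontinuation or exit in SAP 3.1. SAP 11 does not list that change.

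**The concern.** SAP 6.1 already accepts the principle that daily dosing after a nondaily regimen should not be mixed with planned daily dosing. It applies the principle to one of four routes back to QD. Subjects on the other three have lost some protection at challenge or have interrupted dosing. Under protocol 3.1.3 a subject who switches inside ARC004 may also re-escalate from 80, 120 or 160 mg. That is not the same exposure as uninterrupted 300 mg daily maintenance.

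The primary endpoint is the frequency of treatment-related AEs, and the study's purpose is to describe nondaily regimens beside daily ones. If the plan is followed as written, post-switch QD time and events can enter the 3B/3C QD column, the pooled Group 2 QD column and the Overall columns. Cohort 2 has no QD column, so its post-switch events can enter only Overall. Two subjects who resume daily dosing at the same site, one for intolerance and one for an Exit result, would be tabulated differently.

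**Working it through.** **The plan's own figure.** The only sample-size figure for ARC004 (protocol 9.4, SAP 2.4) is an 80% probability of seeing at least one AE among 400 subjects at a rate of 4 per 1,000. 1 − 0.996^400 = 0.799, which agrees. The present point does not depend on it.

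**Does the SAP 6.1 wording reach the other routes?** The protocol ties not tolerating the regimen to Section 7.8.2: one related SAE, one severe related AE, two moderate related AEs on separate occasions, or three consecutive doses not tolerated. An Exit DBPCFC result and missed doses are not on that list. Category 2 is defined by having tolerated the regimen. SAP 6.1 therefore cannot be read to include it, and its reference to study design does not widen it.

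**Does another rule supply a cut?**

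| Place | End point | Cut at the switch? |
|---|---|---|
| SAP 10.1, QD | last QD day in ARC004 | no |
| SAP 10.3, Group 2 TEAEs | 30 days after last dose | no |
| SAP 7.5, EM | last dose before Exit DBPCFC | would serve for post-Exit switchers, but the Group 2 event tables use QD/QOD/BIW periods; gives no date where the Exit DBPCFC is omitted |
| SAP 3.1 | discontinuation or exit | not stated |

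**Size.** Inputs: Cohort 3 planned at 175, split equally three ways, and Cohort 1 at 120 (protocol 7.8.3); 28 weeks of QD in Cohorts 1, 3B and 3C and 56 weeks in 3A (protocol Section 3). Assumed: every planned subject completes the QD block, and the wait for ARC008 is 14 weeks, one resupply interval under protocol 6.3.10.

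- Planned 3B/3C QD: 2 × (175/3) = 116.7 subjects; 116.7 × 28/52 = 62.8 subject-years.
- Planned Cohort 1 QD: 120 × 28/52 = 64.6. Planned 3A QD: 58.3 × 56/52 = 62.8.
- Pooled Group 2 QD: 64.6 + 62.8 + 62.8 = about 190 subject-years.
- Added per 3B/3C switcher: 14/52 = 0.27 subject-years; 0.269/62.8 = 0.43%.
- Five switchers: 1.35/62.8 = 2.1%. Twelve: 3.23/62.8 = 5.1%, or 3.23/190 = 1.7% of pooled QD.

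Range over the assumed wait, for twelve switchers: 2 weeks gives 12 × 2/52 = 0.46 subject-years (0.7% of 62.8); 28 weeks gives 12 × 28/52 = 6.46 (10.3%).

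These are shares of exposure. The change in an event rate also depends on the post-switch event rate, which the documents do not give.

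**The case against.** **The consequence is small.** The analyses are descriptive (SAP 6.4 and 6.5), and the nondaily data are declared hypothesis-generating (SAP 3.1). All events are listed by subject, study period and event, so nothing is lost. For category 1, protocol 3.1.5 expects most repeat up-dosing to take place in ARC008, so few subjects may be bridged in ARC004. All of this stands and limits the weight of the point.

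**Keeping the events in Overall is defensible.** An overall safety endpoint can reasonably include everything up to the last dose. But SAP 6.1 has chosen otherwise for the intolerant group, and no reason is given for treating the other routes differently.

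**A reader might infer a much larger distortion from SAP 10.1.** Taken literally, first to last QD day for a 3B subject with a 14-week wait runs 28 + 4 + 24 + 14 = 70 weeks, against 28 + 14 = 42 weeks of QD actually taken. The excess over plan is 70 − 28 = 42 weeks, or 42/52 = 0.81 subject-years, of which 28/52 = 0.54 is QOD/BIW time. The documents do not support treating this as the intended rule. SAP 10.1 gives QOD and BIW their own first and last dates for the same cohorts, so the literal reading counts the same days twice. SAP 10.3 divides by subject-years at risk in the study period and does not cite the 10.1 duration formula.

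**A reader might also infer a set of competing primary-endpoint windows.** That goes too far. The active treatment period, "ending with the date and time of the last dose of study product in ACR004", is not invoked in SAP 10.3, and SAP 1.3 on database lock says which data the final analysis holds. Neither defines the endpoint. For a completer with no further dosing, the end of EM and exit are separated mainly by the Exit DBPCFC, whose symptoms SAP 10.3 excludes from TEAE summaries. The difference matters only for subjects dosed in ARC004 after the switch.

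**Conclusion.** The SAP 6.1 exclusion is a stated rule with too narrow a scope. Nondaily Group 2 subjects who go to daily AR101 inside ARC004 because of an Exit DBPCFC result below 1043 mg or below 443 mg, or after missed doses, are not covered, and neither SAP 10.1 nor SAP 10.3 separates their later QD time and events.

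The likely effect on exposure is modest: 0.43% of planned 3B/3C QD per switcher, 2.1% for five and 5.1% for twelve. This rests on the planned cohort sizes and an assumed 14-week wait. The numbers of switchers are also assumed, and the true number may be zero. The effect reaches 0.81 subject-years per 3B switcher only under the literal reading of SAP 10.1, which is probably not meant but is not ruled out in words. No hypothesis test depends on these tables, and desensitization response rates do not change. Group 1 is not involved, since SAP 2.3 kept its QD subjects on QD.

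**What to change.** - **SAP 6.1:** apply the existing exclusion to every Group 2 subject who returns to QD after a nondaily regimen, for any reason, naming the Exit DBPCFC result and missed doses. List those events separately and report the number of subjects, their exposure and their events.
- **SAP 10.1 and 10.3:** end the 3B/3C QD period at the last QD dose before the first QOD dose. For switchers, end the tabulated nondaily and Overall periods at the first post-switch QD dose. Keep the 30-day TEAE window for subjects with no further dosing. Subjects who wait for ARC008 on an unchanged regimen need no new rule.
- **SAP 3.1 and 7.5:** end the primary-endpoint window for switchers at that same first post-switch QD dose. This also gives an end date where the Exit DBPCFC is omitted. Record the change from protocol 9.2.1 in SAP 11.

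Cost: a scope change in SAP 6.1, one date rule and its programming; no new visits or data. The downside is that a few post-switch AEs move from tables to listings. The separate count of subjects, exposure and events keeps them visible.
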